12.0 Setting

12.1 Describe all facilities/sites where you will be conducting research procedures. Include a description of the security and privacy of the facilities (e.g. locked facility, limited access, privacy barriers). Facility, department, and type of room are relevant. Do not abbreviate facility names.

NOTE: Examples of acceptable response may be: "A classroom setting in the Department of Psychology equipped with a computer with relevant survey administration software," "The angiogram suite at Buffalo General Medical Center, a fully accredited tertiary care institution within New York State with badge access," or, "Community Center meeting hall."

Response: Data collection will be completed over the phone (surveys, 24-hour dietary recall) with a trained interviewer and in a private location (height/weight and dermal carotenoid measurements) at the community site from which they were recruited.

12.2 *For research conducted outside of UB and its affiliates, describe:*

- *Site-specific regulations or customs affecting the research*
- *Local scientific and ethical review structure*

NOTE: This question is referring to UB affiliated research taking place outside UB, i.e. research conducted in the community, school-based research, international research, etc. It is not referring to multi-site research. UB affiliated institutions include Kaleida Health, ECMC, and Roswell Park Cancer Institute.

Response: In the various VV sites throughout the Northeast, Midwest, and Southeastern regions, the setting will be similar (i.e. churches, community centers, housing; etc). Data collection will be completed over the phone (surveys, 24-hour dietary recall) with a trained interviewer and in a private location (height/weight and dermal carotenoid measurements) at the community site from which they were recruited.

N/A: This study is not conducted outside of UB or its affiliates.

13.0 Community-Based Participatory Research

13.1 *Describe involvement of the community in the design and conduct of the research.*

NOTE: Community-Based Participatory Research (CBPR) is a collaborative approach to research that equitably involves all partners in the research process and recognizes the unique strengths that each brings. CBPR begins with a research topic of importance to the community, has the aim of combining knowledge with action and achieving social change to improve health outcomes and eliminate health disparities.

Response:

N/A: This study does not utilize CBPR.

13.2 *Describe the composition and involvement of a community advisory board.*

Response:

At both the intervention and comparison sites, engagement will focus on involving community members in food access program planning and research. We anticipate each organization will create one or more community advisory committees to oversee their food access work. At intervention sites, these advisory committees will focus on planning for a MM program. At comparison sites, engagement efforts will be more generally centered on food access and understanding what types of programs would be most acceptable.

N/A: This study does not have a community advisory board.

NOTE: One example includes: on-call availability of a counselor or psychologist for a study that screens subjects for depression.

Response: N/A

14.4 Describe your process to ensure that all persons assisting with the research are adequately informed about the protocol, the research procedures, and their duties and functions.

Response: All persons assisting with the research will have current training in UB's Good Research Procedures course and CITI training. The project coordinator will be trained by the PI on all aspects of the research. The project coordinator will train the data collectors using provided protocols.

All research personnel will be adequately informed about the protocol, research procedures, and their duties and functions through individual training provided by the Principal Investigator and project coordinator. All team members will receive appropriate training on maintaining confidentiality and protecting human subjects. Study staff will be assigned duties that are best suited to their qualifications. The Principal Investigator and project coordinator will provide direct oversight of the research staff to ensure proper conduct of research and the protection of subjects' rights and welfare.

Two individuals from each of the 9 Partner Organizations will also be trained in UB's Good Research Procedures course and CITI training. These individuals will be added as external members to the IRB as they come on board. They will only be involved

with helping to recruit and collect in-person data collection (height, weight, veggie meter). When the in-person data is collected, it will be property of the partner organization. Once the participant consents to be in the study, only then will the in-person data be shared with UB research team. The partner organization staff will not have access to REDCap; instead they will collect this information via paper and hand over directly to UB Research Team (See Phase 2 Interest Form).

15.0 Other Approvals

15.1 *Describe any approvals that will be obtained prior to commencing the research (e.g., school, external site, funding agency, laboratory, radiation safety, or biosafety).*

Response:

N/A: This study does not require any other approvals.

16.0 Provisions to Protect the Privacy Interests of Subjects

16.1 *Describe how you will protect subjects' privacy interests during the course of this research.*

NOTE: Privacy refers to an individual's right to control access to him or herself. Privacy applies to the person. Confidentiality refers to how data collected about individuals for the research will be protected by the researcher from release. Confidentiality applies to the data.

Examples of appropriate responses include: "participant only meets with a study coordinator in a classroom setting where no one can overhear", or "the participant is reminded that they are free to refuse to answer any questions that they do not feel comfortable answering."

Response: Conducted over the phone, the consent process and data collection will take place in a private room on the UB campus in Kimball Tower. The PI ([name]), coordinator ([name]), graduate assistant ([name]), and student data collectors (to be named) will be entering data into REDCap. Only the research team will have access to the survey data. In some cases if internet access is not available and a paper copy of the survey is needed, the UB research assistant will keep those copies secure until in Buffalo where they will be entered directly in REDCap and the paper copy will be destroyed. Any paper copies of data that are kept while waiting to be entered will be kept in a locked filing cabinet in a locked office (Kimball 816).

Height, weight, and dermal carotenoid data will be collected in a private room at the community site with only the participant and research team members present during measurement.

When completing surveys over the phone, the UB research assistant will be in a private room and will remind the subject that all information discussed over the phone will be kept confidential. The research assistant will ask the subject to go to a closed or private area in their home while they answer survey questions. Participants will be informed at the start a survey that they can skip any questions that they are not comfortable with. Survey responses and data collection measures will not be shared with anyone at the communities where the MM will take place nor will they be shared with partners who are implementing the MM program. Only the research team will have access to identifiable data.

16.2 Indicate how the research team is permitted to access any sources of information about the subjects.

NOTE: Examples of appropriate responses include: school permission for review of records, consent of the subject, HIPAA waiver. This question does apply to records reviews.

Response: After the consent process, the participant controls the research team's access to the survey data and feedback provided during the program (intervention only) information because it is directly provided by the participant.

During the consent process over the phone, , a study team member will detail all of the elements of informed consent. If the individual decides to participate in the study, they will verbally agree to participate. Consent of the subject will grant permission to the affiliated research team to view information collected during the study.

17.0 Data Management and Analysis

17.1 Describe the data analysis plan, including any statistical procedures. This section applies to both quantitative and qualitative analysis.

Response:

Data Management:

- This study will utilize UB's REDCap (Research Electronic Data Capture) service, a software toolset and workflow methodology for electronic collection and management of clinical and research data, to collect and store data. REDCap provides a secure, web-based application that provides an intuitive data manipulation interface, custom reporting capabilities, audit trail functionality, real-time data monitoring/querying of participant records, and variations of data exporting/importing. REDCap has multiple data export options to common statistical packages (SPSS, SAS, Stata, R/S-Plus). REDCap data collection projects rely on a study-specific data dictionary defined in an iterative self-documenting process. The project specific data dictionary is defined by the research team. As part of the data dictionary development process, individual fields can be denoted as identifiers. When exporting a de-identified dataset, these variables are omitted. Additionally, the data export tool allows for the shifting/removal of dates. All web-based information transmission is encrypted. The data is all stored on a UB private, firewall protected network. All users are given individual user ids and passwords and their access is restricted on a role-specific basis.

- Data collected from participants will be entered by UB researchers into RedCap including: Baseline and 12-month height, weight, dermal carotenoid values, survey data.
- PI ([name]), coordinator ([name]), graduate assistant ([name]), and student data collectors (to be named) will be entering data into REDCap.
- Data will be stored in REDCap, and then extracted into a statistical package for analysis. Extracted data will be stored on the PI's UB School of Public Health and Health Professions encrypted drive .

Data Analysis

Aim 2: In this cluster-randomized study, our primary outcome is change in F&V intake (cups/day) at 12 months using the 24 hour recall, thus, we will compare the difference in mean changes in F&V between intervention and comparison group participants. Our primary analysis will test the hypothesis under the intent-to-treat principle using a Generalized Linear Mixed Model (GLMM) that will account for the correlation induced by the clustering of participants within sites. The GLMM (see below) will include a random intercept for sites (β_0) fixed effects for the baseline value of the primary outcome (β_1) and the intervention (β_2) to test if the differences in mean changes in primary outcomes is zero where β_0 is the fixed intercept and e is error.

$$\text{Change in Primary Outcome}_{9m} = \beta_0 + \beta_1 \text{Primary Outcome}_{baseline} + \beta_2 \text{Intervention} + b_0 + e$$

Including the baseline values score as a covariate in an analysis of covariance (ANCOVA, in our case a GLLM ANCOVA) is known to be a more powerful test than a group comparison of baseline to post-intervention change. In order to further explore the intervention effect, we will fit FLMMs that (1) adjust for baseline covariates of interest; (2) adjust for baseline variables distributed differently between intervention groups; (3) test interaction terms between treatment group and other covariates; and (4) complete sub-group analyses. Specifically, we will look at differences in changes of F&V consumption, perceived access and self-efficacy by intervention usage. Additionally, if we see correlations between changes in F&V consumption, self-efficacy, intervention usage and/or perceived access at 12 months, we will conduct analyses to determine if these changes mediate the intervention effect. In addition, we will expand the regression models by including interaction terms to examine the heterogeneity of intervention and the role of moderators such as organizations or community types.

17.2 If applicable, provide a power analysis.

NOTE: This may not apply to certain types of studies, including chart/records reviews, survey studies, or observational studies. This question is asked to elicit whether the investigator has an adequate sample size to achieve the study objectives and justify a conclusion.

Response: Based on our initial cluster RCT, we estimate the intra-class correlation (ICC) for change in F&V intake to be 0.08 (SD 2.7). We expect the MM program to increase the F&V intake by at least 1 cup/day (effect size of approximately 0.4). Using one-sided tests of significance at $p=0.05$, an $ICC=0.08$, and cluster size=21 participants per site, 12 sites per group will provide at least 90% power to detect the anticipated change in F&V consumption. To account for possible attrition or extended delays on the part of the organization, we will over-recruit. While we need 6 organizations (24 MM sites) to achieve the desired power, we will recruit 9 organizations (33 sites). We expect participant attrition to be no more than 30% based on previous work, so we will plan to recruit about 30 participants per site.

17.3 Describe any procedures that will be used for quality control of collected data.

Response: Research staff will be adequately trained in proper data collection. Collected data will be reviewed by the project coordinator to ensure completeness and accuracy.

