4.0 Study Design

4.1 *Describe and explain the study design (e.g. case-control, cross-sectional, ethnographic, experimental, interventional, longitudinal, observational).*

Response: This Veggie Van effectiveness and implementation study, funded by the NIH, will be overseen by Drs. [name], [name], Co-Investigator, [name], Co-Investigator, and [name], Co-Investigator. This study will be coordinated by project coordinators and staff at UB and UNC.

For Aim 2 of the study, all study related procedures will be carried out by UB staff.

Aim 2: After 9 qualified organizations* have been identified among applicants, we will randomize proposed MM sites (33 total across all partner organizations), to an intervention (MM program implementation) or comparison condition (extended planning). Randomization will be stratified within each organization so that each organization will have 2 intervention and 2 comparison sites. One organization will have 5 sites. The 5th site will allow for more thorough testing of protocol procedures. This ensures that study groups will be balanced at the organizational level. The condition for which each proposed MM location was selected will be communicated at the time of award. Organizations will communicate to intervention sites that they want to open a MM at that location within the next year. Organizations will communicate to comparison sites that they want to work with them on a food systems planning process to determine if a MM program is the right fit for their location. At the end of the year-long planning process with comparison sites, the organization and proposed MM site will decide together how to proceed (start a MM, apply for grant funding for a different project; etc.).

Both arms will undergo community engagement efforts that serve to both identify potential research participants and engage them in the planning for a MM. Intervention sites will work with a community advisory committee to develop an engagement plan to raise community awareness of the forthcoming MM. Comparison sites will work with a community advisory committee to engage community members in a food access planning process.

Both intervention and comparison sites will distribute sign-up forms as part of the community engagement process. UB staff will identify from the sign-up forms those interested in participating in the study. Consent will be obtained via phone. Phone surveys and in-person data collection will then be completed.

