5.0 Local Number of Subjects

5.1 Indicate the total number of subjects that will be enrolled or records that will be reviewed locally.

Response:

Aim 2: We plan to recruit at least 30 participants at each of the 33 proposed sites (990 total).

Sub-study: We are looking to recruit an additional 50 individuals from across all sites.

5.2 If applicable, indicate how many subjects you expect to screen to reach your target sample (i.e. your screen failure rate).

Response: The majority of recruitment will take place over a 2-month community engagement process at each site. During this 2-month process, we anticipate screening at least 100 individuals per site in order to reach our target of 30 participants per site.

- Screen 100 participants per site (3,300 total)
- Enroll at least 30 per site (990 total). If there is a lot of interest at a particular site, we may enroll up to 40 participants at a given site. Our target of 990 participant total for the study will be maintained.

5.3 Justify the feasibility of recruiting the proposed number of eligible subjects within the anticipated recruitment period. For example, how many potential subjects do you have access to? What percentage of those potential subjects do you need to recruit?

Response: While we need 6 organizations (24 sites) to achieve the desired power of at least 80%, we will work with 9 organizations (33 sites) across the north, mid, and south east region to recruit 990 participants. We expect participant attrition to be no more than 30% based on previous work, so we will plan to recruit about 30 participants per site over a 2-month process through community engagement efforts. Participants may also be recruited at their first visit to the MM which would clearly show an intent to shop at the MM (i.e. engage with the intervention) or during community events at the planning sites

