2.1 Sample size calculation

Our primary outcome is change in F&V intake (cups/day) at 12 months using the 24-hour recall, thus, we will compare the difference in mean changes in F&V between intervention and comparison group participants. In the sample size and power analyses, we considered similarity in changes in F&V among participants within a site (intra-class correlation, ICC), and the fact that the intervention is at the site level (54, 55). Based on a previous cluster RCT, we estimated the ICC for change in F&V intake to be 0.08 (SD 2.7); We expect the MM program to increase the F&V intake by at least 1 cup/day (effect size of approximately 0.4). Using one-sided tests of

significance at $p=0.05$, an $ICC = 0.08$, and cluster size = 21 participants per site, 12 sites per group will provide at least 80% power to detect the anticipated change in F&V consumption. To account for possible attrition or extended delays on the part of the organization, we will over-recruit (i.e., select more organizations than needed as part of the RFP process). While we need 6 organizations (24 MM sites) to achieve the desired power (Table 4), we will recruit 8 organizations (32 sites). We expect participant attrition to be no more than 30% based on previous work, so we will plan to recruit about 30 participants per site.

Table 1: Power Calculation

Actual Power ($1-\beta$)	Difference in Mean Change in F&V	No. of Sites Per Study Group	No. of Participants per Site	Sample Size Per Study Group	Sample Size Per Group with 30%
0.80	1.0	12	21	252	328
0.81	1.0	16	11	176	229
0.80	1.0	20	8	160	200
0.80	.75	20	45	900	1285

3. Aims and objectives

To measure MM effectiveness at sites randomized to implement a MM for 1 year versus a planning (control) condition. Measure MM effectiveness at improving the following outcomes between baseline and 1-year follow-up: 1.) self-reported diet measured via two 24-hour dietary recalls, 2.) BMI based on in-person height and weight measurements; 3.) an objective indicator of F&V consumption (dermal carotenoids measured via finger scan) and 4.) Social Cognitive Theory diet-related constructs including self-efficacy and food environment.

4. Outcomes

This section will present outcomes investigated in the RCT to answer the above study aims and objectives.

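### Protocol 17.2 claims at least 90% power for 12 sites per group, but its own inputs give about 80%, the figure stated in the SAP

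*Protocol*

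**What the plan says.** Protocol section 17.2 gives a full set of inputs for the primary outcome, change in fruit and vegetable intake: ICC 0.08, SD 2.7, a difference of at least 1 cup/day (described as an effect size of about 0.4), a one-sided 5% test and 21 participants per site. It concludes that "12 sites per group will provide at least 90% power to detect the anticipated change in F&V consumption". It then calls 24 sites the number needed and the rest over-recruitment against attrition or delay: "While we need 6 organizations (24 MM sites) to achieve the desired power, we will recruit 9 organizations (33 sites" in total).

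Two other places give a lower power for the same 24 sites:

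- Protocol section 5.3: "While we need 6 organizations (24 sites) to achieve the desired power of at least 80" per cent. It gives no SD, ICC or cluster size.
- SAP section 2.1, with the same inputs as protocol 17.2: "12 sites per group will provide at least 80% power to detect the anticipated change in F&V consumption". Row 1 of SAP Table 1 (12 sites per group, 21 per site, difference 1.0) shows a power of 0.80.

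The planned number of sites is larger. Protocol section 4.1 says "we will randomize proposed MM sites (33 total across all partner organizations"), and SAP section 2.1 says "we will recruit 8 organizations (32 sites").

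**The concern.** The protocol attaches two power figures to one minimum design, and the SAP sides with the lower one. Section 17.2 is where the protocol is asked to justify the sample size. It presents the sites beyond 24 as a reserve, so a reader would conclude that the trial could lose all of them and still have 90% power. If the 90% is wrong, the type II risk at that minimum is about twice what is stated, and power near 90% depends on keeping the 8 or 9 extra sites.

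**Working it through.** **Inputs** (protocol 17.2, repeated in SAP 2.1): difference 1 cup/day, SD of change 2.7, ICC 0.08, m = 21 per site, k = 12 sites per group, one-sided alpha 0.05. The 21 is already net of dropout: 30 × 0.7 = 21.

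**Formulas**

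- Design effect = 1 + (m − 1) × ICC = 1 + 20 × 0.08 = 2.6
- SE = SD × √[(design effect / m) × (1/k₁ + 1/k₂)]
- Noncentrality = difference / SE
- Power from the normal distribution, or from the noncentral t with k₁ + k₂ − 2 degrees of freedom

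**The 24-site design**

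- SE = 2.7 × √[(2.6/21) × (1/12 + 1/12)] = 0.388
- Noncentrality = 1 / 0.388 = 2.578
- Power = 0.803 (t, 22 df) or 0.825 (normal)

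The t result reproduces the 0.80 in SAP Table 1, row 1. The same method gives 0.812 for row 2 (16 sites × 11), where the table shows 0.81. So the SAP's figure for this design is recovered and the protocol's is not.

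**Other designs and readings** (one-sided 5%, ICC 0.08)

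| Design | t | Normal |
|---|---|---|
| 12 v 12, 21 per site, as stated | 0.803 | 0.825 |
| 12 v 12, 21 per site, effect size exactly 0.4 | 0.854 | 0.873 |
| 12 v 12, 30 per site (no attrition) | 0.841 | 0.860 |
| 15 v 15, 21 per site | 0.878 | 0.892 |
| 16 v 16, 21 per site (SAP, 32 sites) | 0.897 | 0.909 |
| 17 v 16, 21 per site (protocol, 33 sites) | 0.905 | 0.916 |

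The 17 v 16 split is an assumption about which arm receives the odd site. Power is the same either way. A two-sided test moves further from 90%: 0.693 (t) or 0.732 (normal) for the stated design. With 12 × 21 held fixed, 90% needs an ICC of about 0.04–0.05 or an SD of about 2.30–2.35.

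**Minor: other cells of SAP Table 1.** Rows 3 and 4 both show 0.80. At ICC 0.08 they give 0.831 (20 × 8) and 0.859 (20 × 45, difference 0.75) by t. The last column, headed "Sample Size Per Group with 30" per cent (the rest of the header is not legible in the text available), follows no single attrition formula:

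| n per group | n × 1.3 | n / 0.7 | Table |
|---|---|---|---|
| 252 | 327.6 | 360 | 328 |
| 176 | 228.8 | 251.4 | 229 |
| 160 | 208 | 228.6 | 200 |
| 900 | 1170 | 1285.7 | 1285 |

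The documents do not show which cells are wrong. For row 3, 20 × 7 would give 0.804 and 140/0.7 = 200. For row 4, an assumed ICC of 0.10 would give 0.801. Both are only possible readings.

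**The case against.** The strongest defence is baseline adjustment. Protocol section 17.1 makes a baseline-adjusted mixed model the primary analysis and says that it is more powerful than comparing changes. With equal variances and an unchanged ICC, adjustment multiplies the SD of change by √[(1 + r)/2], where r is the baseline to follow-up correlation. For assumed r of 0.6, 0.5 and 0.4, power at 12 × 21 becomes 0.874, 0.892 and 0.910 (t). The real trial could therefore reach about 90% at 24 sites. But neither document gives r, and section 17.2 bases its calculation on the SD and ICC of change. The supportable claim is that the stated inputs do not give 90%, not that 90% is unattainable.

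Combining 30 per site with an effect size of exactly 0.4 gives 0.886 (t) or 0.903 (normal). That passes 90% only by the normal approximation and only by replacing the stated inputs.

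Three other points have some force:

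- At least 80% does not strictly exclude 90%. However, SAP Table 1 labels its 0.80 as actual power.
- The correct figure already stands elsewhere, and SAP section 6 reports analyses in the past tense, so a fall to 24 sites may no longer be a live risk. This limits the practical harm but does not make the figure right.
- Phase 2 recruits have no baseline recalls (protocol section 10.1), so a site that needs them may yield fewer than 21 participants with a computable change. That is a separate problem. It means that every power figure here, including those for 32–33 sites, is conditional on 21 evaluable per site.

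**Conclusion.** The 90% in protocol 17.2 is wrong as written. The stated inputs give 0.803 (t) or 0.825 (normal), so the type II risk at 24 sites is 0.18–0.20 rather than 0.10 or less. The figure of at least 80% in protocol 5.3 and SAP 2.1 is right, and the 24-site minimum stands for that power. The target of 30 per site is consistent with 21 evaluable at 30% attrition. About 90% belongs to the planned trial: 0.897–0.909 with 32 sites and 0.905–0.916 with 33. These results rest on the plan's own SD, ICC, difference and one-sided 5% level, equal cluster sizes, 21 evaluable per site and no gain from baseline adjustment. This is an error in the stated power, not evidence that the planned trial is too small.

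**What to change.** In protocol 17.2, change the stated power at 12 sites per group from at least 90% to at least 80%, so that it agrees with protocol 5.3 and SAP 2.1. If the sponsor wants to quote a higher figure, state it as about 90% for the planned 32–33 sites, on condition of 21 evaluable participants per site. Leave the 24-site minimum and the 30-per-site target as they are.

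As a minor item, recheck rows 3 and 4 and the last column of SAP Table 1, and state the ICC and the attrition formula behind the table. No replacement values are proposed, because the documents do not show which entries are in error.

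The cost is one corrected figure in the protocol, a check of a few table cells, and a less favourable stated power at the minimum number of sites. Recruitment, sites, data collection and analysis do not change.
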